### 2.4. Secondary objectives

The following secondary objectives will be assessed. Unless otherwise stated, the objectives will be addressed separately for adults and children:

- To compare the groups given the Ad26.ZEBOV prime vaccine and the rVSVΔG-ZEBOV-GP prime vaccine (both rVSVΔG-ZEBOV-GP groups combined) each with the pooled placebo group for the antibody response 14 days after randomization (prime vaccination) (immediacy of response).
- To compare each of the vaccine groups versus the pooled placebo group for the antibody response profile using measurements at 7, 14, 28, 56, 63 days and at 3, 6 and 12 months after randomization.
- To compare each of the vaccine groups with the pooled placebo group for SAEs at 12 months (see section [4.1.3](#)).
- To compare the groups given the Ad26.ZEBOV prime vaccine and the rVSVΔG-ZEBOV-GP prime vaccine (both rVSVΔG-ZEBOV-GP groups combined) each with the pooled placebo group for the percent with injection site reactions and AEs graded for severity, including targeted symptoms, during the first week following randomization (including the daily contacts for children only).
- To compare the groups given the Ad26.ZEBOV prime vaccine and the rVSVΔG-ZEBOV-GP prime vaccine (both rVSVΔG-ZEBOV-GP groups combined) each with the pooled placebo group for percent reporting injection site reactions and AEs graded for severity, including targeted symptoms, following prime vaccination at the vaccination visit, and through 7, 14, and 28 days after the prime vaccination.

- To compare each of the vaccine groups with the pooled placebo group for changes from baseline in biochemical markers and complete blood count (CBC) measurements at 7 days after randomization (children only).
- To compare the rHAd26/MVA and rVSVΔG-ZEBOV-GP boost strategies with the pooled placebo group for changes from baseline in biochemical markers and CBC measurements at 63 days after randomization (children only).
- To compare the rHAd26/MVA and rVSVΔG-ZEBOV-GP boost strategies with the pooled placebo for percent with injection site reactions and AEs graded for severity, including targeted symptoms, immediately following the booster vaccination and through month 3 (approximately 35 days after the booster vaccination).
- To compare the three vaccine strategies versus the pooled placebo group for long-term antibody response at 24, 36, 48 and 60 months following randomization (if funding permits).

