Prior to carrying out the endpoint analyses which pool the two placebo groups, the two placebo groups will be compared for the immunogenicity and safety outcomes. The primary analyses for adult and children will be carried out at the 0.0167 (2-sided) level of significance and will compare the three vaccine strategies with the pooled placebo group for the percent with a positive antibody response at 12 months. Each pair-wise comparison will be carried out using Mantel-Haenszel chi-square statistics which consider stratification by vaccination center. Similar methods will also be used to compare groups for the immediacy of the antibody response at 14 days. These analyses will exclude those participants with elevated antibody levels at baseline. Participants will not be screened at study entry for elevated antibody levels. These exclusions will be carried out during analysis. Analyses will also be carried out for all randomized participants irrespective of antibody level at baseline.

Similar methods will be used to compare antibody responses of each vaccine strategy with the pooled placebo group at other time points, including 28 days after randomization and 28 days following the booster vaccination. The two additional primary objectives for immune responses, pooled rVSVΔG-ZEBOV-GP groups versus pooled placebo groups 28 days after randomization for Merck, and rHAd26/MVA versus pooled placebo groups approximately 28 days following

booster vaccination for Janssen, will be carried out the 0.05 (2-sided) level of significance.

All comparisons (for adults, children, and for adults and children combined) of immune responses and safety outcomes at other time points will be carried out at the 0.0167 (2-sided) level of significance when there are three pair-wise comparisons made (e.g., each vaccine strategy versus pooled placebo) and at the 0.025 (2-sided) level of significance when there are two pair-wise comparisons made (e.g., for comparisons at days 7, 14, 28 and 56 with the pooled placebo group in which the two rVSVΔG-ZEBOV-GP strategies are pooled).

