SAEs will be classified by system organ class according to MedDRA®. The total number of events and the number of participants with at least one event will be reported. Mantel-Haenszel chi-square statistics will be used for each pair-wise comparison of the number of participants with an SAE through 12 months of follow-up; time-to-event methods, e.g., Kaplan-Meier, Cox regression, will also be used to compare groups for SAEs over the 12 month follow-up period. Analyses will also be carried out for SAEs judged to be related to the vaccine. If follow-up is extended to 60 months, similar analyses will be performed for SAEs reported through 60 months.

Each vaccine group will be compared with the pooled placebo group using Mantel-Haenszel chi-square tests and time-to-event methods for diagnoses of laboratory-confirmed malaria through 12 months of follow-up.

For safety and efficacy outcomes assessed before the booster at 56 days, the two groups given the rVSVΔG-ZEBOV-GP prime vaccination will be combined for comparisons with pooled placebo group. For outcomes that are assessed after 56 days, each of the three vaccination strategies will be compared with the pooled placebo group.

Mantel-Haenszel chi-square tests will be used to compare each vaccine with placebo for the percent with grade 3 or 4 AEs and with targeted symptoms reported at 7, 14, and 63 days. Similar methods will be used to compare injection site reactions reported immediately following prime vaccination and at 7 and 14 days. Likewise, treatment differences in injection site reactions reported immediately following booster vaccination and through day 63 (7 days after booster vaccination) will be summarized with similar methods. In the event that there is evidence that safety outcomes differ between the two placebo groups, analyses will also be performed for each vaccine versus its matched placebo.

Longitudinal mixed models will be used to compare log-transformed antibody levels collected at multiple follow-up time points during follow-up. Results will be summarized as geometric means and geometric mean ratios. These analyses will be carried out among participants who did not have elevated antibody levels at baseline. Baseline titer level will be included as a covariate. These analyses will be supplemented with scatter plots that display fold increases in antibody titers, line plots, box plots and reverse cumulative distributions of antibody levels at each visit for each vaccine group.

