## 2 Study Design Overview and Protocol History

### Version 1.0 of the PREVAC Protocol

Version 1.0 of PREVAC described the plan to compare three vaccine strategies with placebo in adults and children for immunogenicity and safety. The three vaccine strategies were:

- 1) Ad26.ZEBOV (prime) (0.5 mL) followed by an MVA boost (0.5 mL) at 56 days;
- 2) rVSV (prime) (1 mL) with a placebo (1 mL) boost at 56 days; and
- 3) rVSV (prime) (1 mL) with a rVSV boost (1 mL) at 56 days.

There were two placebo groups, one with a syringe fill volume of 0.5 mL to match the fill volumes of the Ad26.ZEBOV and MVA vaccines and the other with a fill volume of 1 mL to match the fill volume for the rVSV vaccine. We referred to this plan as the 5-arm randomization.

Version 1.0 of PREVAC was not implemented.

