#### **2.1.5.5 Injection site reactions, targeted symptoms and grade 3 or 4 adverse events at scheduled follow-up visits following prime vaccination**

The number and percentage of participants who report an injection site reaction (any redness or swelling induration) within 30 minutes after prime vaccination (baseline), one week after prime vaccination (day 7), 2 weeks after prime vaccination (day 14), and one month after prime vaccination (day 28) will be summarized. Similarly, the number and percentage of participants who report an injection site reaction 30 minutes after booster vaccination (day 56), one week after booster vaccination (day 63), and one month after booster vaccination (month 3) will be summarized by vaccine group. For these analyses, proportions will be compared between each vaccine strategy and the pooled placebo using the Mantel Haenszel chi-square test stratified by site.

For safety outcomes, comparisons may also be made between each active vaccine and its matching placebo.

Pain/tenderness with activity, itching at injection site, and targeted symptoms are graded as not present or grade 1-4. For each of these, the number and percent of participants with each reported symptom or any of the symptoms will be summarized. For each symptom, the number and percent with each grade will also be summarized. Participants with unsolicited symptoms will be listed. The percent with fever (body temperature > 38.0 °C) will also be summarized. These summaries will be carried at the time points mentioned above. For these analyses, proportions will be compared between each vaccine strategy and the pooled placebo using the Mantel Haenszel chi-square test stratified by site. Comparisons may also be made between each active vaccine and its matching placebo.

**Note: Analyses of safety data after day 56 will be carried out on all participants, including those who did not receive the booster vaccination. As previously noted, a very high percentage of participants received the booster vaccination. Among participant who did not receive the booster, most did not complete questions concerning symptoms at Day 63 and 3 months.**

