#### **2.1.5.8 Complete blood count and serum chemistries**

Complete blood counts and serum chemistries were measured for children using blood collected at baseline, day 7 and day 63. Laboratory tests were carried out at the vaccination site.

Results will be summarized by vaccine group. At day 7 and day 63 (7 days after the booster vaccination), change from baseline will be summarized by vaccine group, and compared between each active vaccine group and placebo using a linear regression model with vaccine indicators, adjusted for baseline levels. For each vaccine versus placebo comparison, the estimated mean difference, the standard error (SE) of the difference and P-value will be provided. For the analyses using day 7 results, the two rVSV groups will be combined.

All of these analyses will be stratified by site (local site laboratory).

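### SAP 2.1.5.5 and 2.1.5.6 leave out the protocol's rule that the two rVSV arms are combined for reactogenicity assessed before the day-56 booster

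*SAP*

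**What the plan says.** SAP 2.1.5.5 covers reactions and symptoms within 30 minutes of the prime and at days 7, 14 and 28, and then after the booster at day 56, day 63 and month 3. For all of these visits, "proportions will be compared between each vaccine strategy and the pooled placebo using the Mantel Haenszel chi-square test stratified by site". The section gives no pooling instruction and no significance level. SAP 2.1.5.6 has the children's daily diary summarized in the same way, so its post-prime week inherits the instruction.

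The SAP's list of strategies (section 2, Version 1.0) separates the two rVSV arms: item 2 reads "rVSV (prime) (1 mL) with a placebo (1 mL) boost at 56 days; and" and item 3 is the same prime with an rVSV boost. SAP 2.1.4 counts three strategies at 12 months.

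Elsewhere the SAP states pooling where it is wanted. Section 2.1.4 combines the rVSV arms for antibody results at days 7 to 56, and section 2.1.5.8 does so for laboratory safety: "For the analyses using day 7 results, the two rVSV groups will be combined".

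The protocol has an explicit rule. In section 2.4, the first-week reactogenicity objective compares the prime groups with "both rVSVΔG-ZEBOV-GP groups combined) each with the pooled placebo group for the percent with injection site reactions", and the next objective repeats this through day 28. Section 7.1 says that for safety and efficacy outcomes before the booster "the two groups given the rVSVΔG-ZEBOV-GP prime vaccination will be combined for comparisons with pooled placebo group". It also sets the levels: "at the 0.0167 (2-sided) level of significance when there are three pair-wise comparisons made" and "at the 0.025 (2-sided) level of significance when there are two pair-wise comparisons made".

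**The concern.** Before day 56 the two rVSV arms are one exposure, so there is one prime-dose effect to estimate. An analyst who follows 2.1.5.5 to the letter would split about 600 recipients per age population into 400 and 200, run three comparisons with placebo where the protocol plans two, and be left without a stated level. The cost is precision and power on outcomes that matter here. Joint pain and joint swelling are targeted symptoms (protocol 4.3.1.1), and arthritis is the reason rVSV was left out of Version 2.0.

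**Working it through.** **Inputs.** Allocation 2:1:2:1:1 with about 1,400 per age population (protocol 2.7 and 2.9; SAP section 2 reports 1,401 adults and 1,401 children). This gives about 400 rVSV without boost, 200 rVSV with boost and 400 pooled placebo. Levels are 0.025 for two comparisons and 0.0167 for three (protocol 7.1). The documents give no planning rates for reactogenicity, so the rates below are assumptions.

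**Formula.** Two-proportion normal approximation, unstratified: power = Φ[(|p1 − p0| − z·s0)/s1]. Here s0 = √{p̄(1 − p̄)(1/n1 + 1/n0)}, s1 = √{p1(1 − p1)/n1 + p0(1 − p0)/n0}, and p̄ is the pooled rate.

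**Reproducing the plan.** Protocol 2.7 gives power 0.88 for SAEs of 5% versus 12%, 400 per group, at 0.0167. With p̄ = 0.085, s0 = 0.0197, s1 = 0.0196 and z = 2.393, (0.070 − 0.0472)/0.0196 = 1.17, so power is 0.878. This agrees. The companion figure of 0.86 (5% versus 14%, 200 versus 400) comes out at 0.896 by the same formula, and at 0.861 if 10% are lost.

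**10% versus 5%, per age population.**
- Combined, 600 v 400 at 0.025: p̄ = 0.080, s0 = 0.0175, s1 = 0.0164, z = 2.241; (0.050 − 0.0392)/0.0164 = 0.66, power 0.74.
- 400 v 400 at 0.0167: p̄ = 0.075, s0 = 0.0186, s1 = 0.0185; (0.050 − 0.0446)/0.0185 = 0.29, power 0.62.
- 200 v 400 at 0.0167: p̄ = 0.067, s0 = 0.0216, s1 = 0.0239; (0.050 − 0.0517)/0.0239 = −0.07, power 0.47.

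| Assumed rates (rVSV v placebo) | Combined, 0.025 | 400 arm, 0.0167 | 200 arm, 0.0167 |
|---|---|---|---|
| 5% v 1% | 0.91 | 0.82 | 0.70 |
| 10% v 5% | 0.74 | 0.62 | 0.47 |
| 30% v 20% | 0.91 | 0.81 | 0.63 |
| 4.5% v 3.2% | 0.11 | 0.08 | 0.07 |
| 35% v 20% | 0.999 | 0.99 | 0.94 |

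The 4.5% and 3.2% are the arthritis rates in the Phase 1b dose-response trial described in protocol 1.1.3.

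**Source of the loss.** It is not only the level. With 0.025 throughout, 10% versus 5% gives 0.74 against 0.67 and 0.53.

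**Precision of the difference from placebo.** At 10% versus 5%, s1 falls by 12% against the 400 arm (0.0164/0.0185) and by 31% against the 200 arm (0.0164/0.0239).

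**Agreement of the split tests.** In 200,000 simulated trials with one common true effect, the two separate tests disagreed on significance in 38% at 10% versus 5% and in 33% at 30% versus 20%. The two rVSV percentages differed on average by about 2 and 3 points, which is sampling error.

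**The case against.** **The rule already exists.** Protocol 2.4 and 7.1 state it, and nothing in the SAP withdraws it. SAP 2.1.4 itself uses the phrase *each vaccine strategy* for a comparison in which the rVSV arms have just been combined, so the phrase does not exclude pooling. This stands. A reader might infer that the SAP has decided to split the arms, and the text does not show that. But 2.1.4 uses the phrase after stating the combination, and 2.1.5.5 never states it. The number of tests and their level are therefore left open.

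**Conflicting estimates.** A reader might expect the split to produce contradictory results. It would produce two noisier estimates of one quantity, which may fall on different sides of a significance threshold.

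**28-day SAEs.** A reader might extend the point to SAP 2.1.5.1. That section only summarizes SAEs through 28 days. Its p-values belong to the 12-month SAEs, where separate strategies are what the protocol plans.

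**The size is selective.** This stands in part. For a very small difference (4.5% v 3.2%) pooling rescues nothing, and for common reactions (35% v 20%) power exceeds 0.9 either way. In adults and children combined, 5% versus 1% gives above 0.99 combined against 0.99 and 0.94.

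**Conclusion.** The point holds as an omission. For injection-site reactions, targeted symptoms and fever at baseline and days 7, 14 and 28, and for the post-prime diary, a literal reading of the SAP departs from the protocol's pooling rule. It does not hold for visits from the booster onward, including the 30-minute observation on day 56, where separate comparisons are correct.

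At the assumed rates where power is neither negligible nor near 1, splitting costs about 9 to 13 points for the 400 arm and 21 to 28 points for the 200 arm, within one age population. These figures rest on assumed event rates, on planned arm sizes without loss, and on applying the protocol's 0.0167 to the three split tests, because SAP 2.1.5.5 names no level.

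**What to change.** Add to SAP 2.1.5.5, and repeat or cross-reference in 2.1.5.6: for outcomes assessed at visits or diary days before the day-56 booster visit, the two rVSV groups are combined and two comparisons with pooled placebo are made at 0.025 (2-sided); from the booster onward the three strategies are compared separately at 0.0167. The individual rVSV arms may still be shown descriptively before day 56.

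The rule should be tied to the visit, not to receipt of the booster, so that it also covers those never boosted: 1,401 − 1,325 = 76 adults and 1,401 − 1,372 = 29 children (SAP 2.1.3).

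No change to 2.1.5.1 is needed. The cost is a few lines of text and no new data. The SAP says it was prepared before unblinding, which is the right stage for the clarification.

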#### **2.1.5.6 Daily diary for children**

For children, injection site reactions, targeted symptoms of any grade severity and

unsolicited grade 3 or 4 adverse events are assessed each day during the week following prime and booster vaccination. The daily diary results will be summarized as described in the previous section. In addition, the number and percent of children reporting the different events at least once will be summarized.

#### **2.1.5.7 Pregnancies**

The number of pregnancies discovered in the first 30 days after the prime or booster vaccination, and the outcomes of these pregnancies, will be summarized by vaccine group.

#### **2.1.5.8 Complete blood count and serum chemistries**

Complete blood counts and serum chemistries were measured for children using blood collected at baseline, day 7 and day 63. Laboratory tests were carried out at the vaccination site.

Results will be summarized by vaccine group. At day 7 and day 63 (7 days after the booster vaccination), change from baseline will be summarized by vaccine group, and compared between each active vaccine group and placebo using a linear regression model with vaccine indicators, adjusted for baseline levels. For each vaccine versus placebo comparison, the estimated mean difference, the standard error (SE) of the difference and P-value will be provided. For the analyses using day 7 results, the two rVSV groups will be combined.

All of these analyses will be stratified by site (local site laboratory).

#### **2.1.5.9 Weight and mid-upper arm circumference for children**

Weight and arm circumference changes will be summarized for children using a linear regression models with vaccine indicators, adjusted for baseline level, age and site.

#### **2.1.6 Subgroup analyses**

The effects of each vaccine strategy compared to placebo on SAEs, injection site reactions, targeted symptoms and the percent of participants with a positive antibody response at 12 months will be assessed for subgroups defined by age (1-4, 5-11, 12-17, 18-29,  $\geq 30$ ) gender, country, site (vaccination center), laboratory performing serology, and HIV status.

These analyses will be conducted using logistic or Cox proportional hazards regression models that include interaction terms for the vaccine group and the subgroup variable. The interaction p-value for age will be assessed both with categorical age (4df) and continuous age (1df). Hazard ratios or odds ratios (each vaccine group versus placebo) and 95% confidence intervals (CIs) will be cited as well as the p-value for the interaction.
